7.1. Adverse Events

A TEAE is an AE with an onset date and time on or after the date of the first dose of study drug and within the 14 days after the date of the last dose of study drug. If the AE onset date and time are unknown, it will be assumed that the AE is a TEAE. If the AE onset time is unknown but the AE onset date is the same date as the first dose of study drug, it will be assumed that the AE is a TEAE. See details for imputing missing/partial start dates (Section 4.3.4.1).

TEAEs, categorized by MedDRA system organ class (SOC) and/or preferred term (PT), will be summarized in frequency tables. The frequency tables will include the number and percentage of unique subjects experiencing each event one or more times by treatment group.

An overall summary table will be provided which summarizes the number and percentage of unique subjects with any TEAE, treatment-emergent SAE, TEAE leading to study drug dose reduction, TEAE leading to study drug withdrawn, TEAE leading to study discontinuation, and TEAE resulting in death. The summary table will also include the frequency distribution of the maximum TEAE intensity (mild, moderate, severe) reported for each subject.

The following summary tabulations will also be presented by treatment group. Unless otherwise noted, the tables will be sorted in alphabetical order. The first line of the table will display the number and percentage of subjects with at least one of the following adverse event categories:

- TEAEs, classified by SOC and PT
- Any TEAEs, classified by PT, displayed in a descending order by frequency in the NBI-921352 group
- Treatment-emergent SAEs by SOC and PT
- TEAEs leading to study drug withdrawn by SOC and PT
- TEAEs leading to study discontinuation by SOC and PT
- TEAEs leading to death by SOC and PT

Separate listings of TEAEs resulting in study drug dose reductions, SAEs, and fatal AEs will also be provided. In the event that no subjects experience study drug dose reductions, SAEs, or

fatal AEs, the blank listing shell will be presented with text printed in the center of the listing describing that no adverse events of that type occurred during this study.

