10. ADVERSE EVENTS

All AEs, whether observed by the investigator, reported by the subject, noted from laboratory findings, or identified by other means, will be recorded from the time the subject has signed the ICF until the subject's final study visit (or upon early termination).

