10.1. Definition

An AE is any untoward medical occurrence in a patient or clinical investigation subject administered a pharmaceutical product and which does not necessarily have to have a causal relationship with this treatment. An AE can therefore be any unfavorable and unintended sign

(including an abnormal laboratory finding, for example), symptom, or disease temporally associated with the use of a medicinal product, whether or not considered related to the medicinal product.

AEs include, but are not limited to, any of the following:

- worsening or change in nature, severity, or frequency of conditions present at the start of the study
- subject deterioration beyond what would be expected due to the primary illness
- intercurrent illness
- drug interaction

All suicidal behaviors and clinically significant suicidal ideations will be documented as an AE.

Subjects should be questioned in a general way, without asking about the occurrence of any specific symptom. The investigator should attempt to establish a diagnosis of the event based on signs, symptoms, and/or other clinical information. In such cases, the diagnosis should be documented as the AE and not the individual signs/symptoms. Following questioning and evaluation, all AEs, whether believed by the investigator to be related or unrelated to the study treatment, must be documented in the subject's medical records, in accordance with the investigator's normal clinical practice and on the AE eCRF. Each AE is to be evaluated for duration, intensity, frequency, seriousness, outcome, other actions taken, and relationship to the study treatment.

The following are not considered AEs:

- Continuous persistent disease/symptom present before drug administration, unless it unexpectedly progresses, or increases in severity following drug administration.
- Treatment failure or lack of efficacy
- Seizures will not be considered an AE unless there is a significant increase in seizure frequency, a new seizure type, occurrence of status epilepticus, and/or in the investigator's opinion it should be captured as an AE.
- Pregnancy
- Overdose of either study treatment or concomitant medication without any clinical signs or symptoms.

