10.1.1. Intensity of Adverse Events

AEs must be graded for intensity. An intensity category of mild, moderate, or severe, as defined in [Table 5](#), must be entered on the AE eCRF. It should be noted that the term "severe" used to grade intensity is not synonymous with the term "serious."

Table 5: Intensity of Adverse Events

Grade	Intensity
Mild	An adverse event that is usually transient and may require only minimal treatment or therapeutic intervention. The event does not generally interfere with usual activities of daily living.
Moderate	An adverse event that is usually alleviated with additional specific therapeutic intervention. The event interferes with usual activities of daily living, causing discomfort but poses no significant or permanent risk of harm to the research subject.
Severe	An adverse event that interrupts usual activities of daily living, or significantly affects clinical status, or may require intensive therapeutic intervention.

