10.2. Recording Adverse Events

For randomized subjects, each AE will be listed as a separate entry on an AE eCRF. Screen failure subjects will have AE information noted only in the source document. The investigator (or designee) will provide information on dates of onset and resolution, intensity, seriousness, frequency, action(s) taken, changes in study treatment usage, relationship to study treatment, and outcome.

The following categories of medical events that could occur during participation in a clinical study must be reported within 24 hours to NBI or its designee:

- SAE, including death (must be reported immediately and no later than 24 hours under any circumstances)
- Pregnancy
- Treatment unblinding for any reason.
- Events of suicidal behavior or suicidal ideation type 4 (active suicidal ideation with some intent to act, without specific plan) or type 5 (active suicidal ideation with specific plan and intent) based on the C-SSRS.

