Safety	A TEAE is an adverse event that started or worsened in severity following the first dose of study treatment. Subject incidence of TEAEs, serious TEAEs, TEAEs leading to discontinuation of study treatment, fatal TEAEs, and adverse events of special interest will be summarized for each treatment group by system organ class and preferred term. Clinical laboratory, vital signs, ECG, weight, height/length, Tanner stage, C-SSRS, [REDACTED] at baseline and during treatment, and the changes from baseline, will be summarized for each treatment group using descriptive statistics. The incidence of potentially clinically significant laboratory values will be provided. Categorical shift tables for selected laboratory values may also be presented.
PK	The plasma concentration data for NBI-921352 and metabolites will be summarized by sampling time point using the PK Analysis Set. [REDACTED]

ASM=antiseizure medication; BLQ=below the level of quantification; C-SSRS=Columbia-Suicide Severity Rating Scale; ECG=electrocardiogram; PK=pharmacokinetics; SAP=statistical analysis plan; TEAE=treatment-emergent adverse event; VABS-3=Vineland Adaptive Behavioral Scales-3.

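### The SAP defines treatment-emergent events by onset alone, drops the protocol's worsening criterion, and does not record the change in the visible text of Section 9

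*SAP*

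**What the plan says.** The two documents define a treatment-emergent adverse event (TEAE) differently.

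- Protocol 11.4, Table 9 (Safety row): "A TEAE is an adverse event that started or worsened in severity following the first dose of study treatment". It has two criteria, start or worsening, and no end to the window.
- SAP 7.1: "A TEAE is an AE with an onset date and time on or after the date of the first dose of study drug". This is a single criterion, onset. The same sentence then adds an upper limit, under which onset must fall "within the 14 days after the date of the last dose of study drug".

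The recording rules are in the protocol. Section 10 says that AEs "will be recorded from the time the subject has signed the ICF until the subject's final study visit", so events before the first dose are in the database. Section 10.2 says that "each AE will be listed as a separate entry on an AE eCRF", and Section 10.1.1 asks for one grade for each: "An intensity category of mild, moderate, or severe". Among the things Section 10.1 does not count as AEs is this: "Continuous persistent disease/symptom present before drug administration, unless it unexpectedly progresses, or increases in severity following drug administration". A pre-existing symptom that gets worse on drug is therefore an AE.

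Every table in SAP 7.1 is restricted to TEAEs. Beyond the tables, "Separate listings of TEAEs resulting in study drug dose reductions, SAEs, and fatal AEs will also be provided". No listing of all AEs is planned. The visible part of SAP Section 9 reports the termination, the synoptic report, the restriction to selected Sentinel Cohort data and the omission of efficacy. It does not mention the TEAE definition.

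**The concern.** Protocol Section 11 leaves technical detail to the SAP, but removing one of two qualifying criteria changes which events count. A reader of the report who knows the protocol would assume that worsening on drug is included.

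The definition carries more weight than usual here. SAP Section 7 will not summarise vital signs, ECGs, laboratory tests, examinations or the C-SSRS, and relies on the AE summaries to show significant changes from baseline. Efficacy is not analysed either, so a rise in seizure frequency that qualifies as an AE has no other planned summary. Worsening of something already present is a change from baseline, and it is the kind of event the onset-only rule can miss.

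**Working it through.** No figure in the plan is at issue, so the check compares the definitions and then traces one test case through the planned outputs.

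**1. Is there a pre-dose recording window?** Yes. AE recording begins at consent (Protocol 10), and at least 28 days of baseline diary are required before randomization (Protocol 9.2.1).

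**2. What happens when a pre-dose event worsens on drug?** There are two recording routes.

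| Route | Onset on the eCRF | Protocol Table 9 | SAP 7.1 |
|---|---|---|---|
| Worsening entered as a new AE | after first dose | TEAE | TEAE |
| Earlier entry kept as the only one | before first dose | TEAE (worsened) | not a TEAE |

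No visible text requires or forbids the second route for an AE already entered between consent and first dose.

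**3. Where does the second-route event appear?** The test case is a non-serious, non-fatal AE with a known onset before the date of first dose, kept as one entry, whose severity rises on drug. The listings sentence is read as three listings, with those of SAEs and fatal AEs not limited to TEAEs.

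| SAP 7.1 output | SAP rule |
|---|---|
| Overall summary, including maximum intensity | absent |
| TEAEs by SOC and PT | absent |
| TEAEs by PT, descending frequency | absent |
| Treatment-emergent SAEs | absent |
| TEAEs leading to drug withdrawal | absent |
| TEAEs leading to study discontinuation | absent |
| TEAEs leading to death | absent |
| Listing: TEAEs with dose reduction | absent |
| Listing: SAEs | absent (non-serious) |
| Listing: fatal AEs | absent (non-fatal) |

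The event is in 0 of 10 outputs. Under the protocol definition it would be in at least 3: the overall summary and the two general TEAE tables. It would be in more if it led to dose reduction, drug withdrawal or study discontinuation.

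**4. Scale.** The planned Sentinel Cohort is 8 subjects randomized 1:1 (SAP Section 3), so 8 / 2 = 4 per arm.

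- One affected subject, second route: 1/4 = 25.0 percentage points in that event's row for the arm.
- The any-TEAE row moves by 25.0 points in the arm (1/8 = 12.5 points over both arms) only if this is the subject's sole TEAE.
- Maximum intensity moves only if this is the subject's worst event.
- First route: 0/4 = 0 points.

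**5. The upper limit.** Subjects who stop dosing are asked to remain for safety assessments to Week 16 (Protocol 8), and AEs are recorded to the final visit. A non-serious AE starting more than 14 days after the last dose is a TEAE under Table 9 but falls outside every SAP 7.1 output.

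**The case against.** The strongest reply is that the protocol already points to a new entry. Section 10.1 lists worsening of conditions present at study start among the things that are AEs, its exception for persistent symptoms also reaches those arising before drug administration, and Section 10.2 gives each AE its own entry. On that reading the worsening has its own post-dose onset and the SAP captures it. This is the more natural reading, but no sentence requires it for an AE already on the eCRF, so the gap narrows without closing.

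A second reply is that restoring the criterion may achieve little. The visible text asks for an intensity grade per AE and does not mention dated changes in grade, so a rise within a single entry may not be identifiable. That stands, and it is why the flagged listing is needed as well as the definition.

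Third, SAP 7.1 states its rule openly, Section 9 speaks of selected safety data, and a post-dose window can be seen as technical detail. But a reader has to compare the two documents to find the difference, and general wording about selected data does not say that a definition changed. Part of Section 9 and the rules for imputing AE start dates are blacked out, so the point is confined to visible text.

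Finally, some rules lean towards inclusion: an unknown onset counts as treatment-emergent, and so does an onset on the first-dose date with unknown time. Reasons for stopping appear in the disposition table, though without identifying the event. These do not help an event whose onset is known to precede the first-dose date.

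**Conclusion.** The concern holds and is minor. The mismatch is plain in the text: SAP 7.1 is narrower than Protocol Table 9 at both ends, and the visible part of Section 9 discloses neither difference.

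The loss from dropping the worsening criterion is conditional. It needs a non-serious event with a known pre-dose onset, kept as a single entry when it worsens. How many such events exist depends on eCRF practice that the documents do not give, and the number may be zero. The 25-point figure shows only what one subject weighs in an arm of 4; it does not estimate how often this happens.

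The stakes are also limited by the terminated study, the planned size of 8, the purely descriptive safety analysis, and the separate listings of serious and fatal events.

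**What to change.** 1. In SAP 7.1, define a TEAE as an AE whose onset, or whose increase in severity, falls on or after the first dose, in line with Protocol Table 9.
2. Before database lock and while still blinded, review AEs ongoing at first dose. Flag those whose intensity rose after dosing, using dated intensity or a new entry where either exists.
3. Add one listing of all AEs with a TEAE flag. It keeps visible any event whose rise cannot be dated and any event after the 14-day limit.
4. Record the 14-day window in SAP Section 9 as a difference from the protocol.
5. If the onset-only rule is kept, say in Section 9 that it departs from Table 9 and that post-dose worsening is expected to be entered as a new AE.

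The cost is a sentence in SAP 7.1, a short entry in Section 9, one blinded check and one listing, for a cohort planned at 8 subjects. The drawback is that a few background events may enter the tables, which the protocol definition already accepts.

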3.1. Randomization

On Day 1, eligible subjects will return to the study center for collection of baseline safety and efficacy assessments. Subjects who continue to be eligible for the study will then be randomized 1:1 (NBI-921352:placebo) via an interactive web response system.

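### SAP 7.1 sets AE onset date and time against only the date of first dose, so as worded a Day 1 event that began before dosing counts as treatment-emergent; the wording is inconsistent and the effect is small.

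*SAP*

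**What the plan says.** SAP 7.1 (Adverse Events) gives the rule that a TEAE is "an AE with an onset date and time on or after the date of the first dose of study drug", up to 14 days after the date of the last dose. No time of first dose is named. The same paragraph covers incomplete onsets. An event with unknown onset date and time is taken to be a TEAE, and so is one that meets this condition: "If the AE onset time is unknown but the AE onset date is the same date as the first dose of study drug". It then points to SAP 4.3.4.1 for start-date imputation, where the individual rules are redacted.

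Protocol 11.4, Table 9 (Safety) has a different definition: "A TEAE is an adverse event that started or worsened in severity following the first dose of study treatment". It excludes a pre-dose onset that does not worsen, and it includes worsening, which SAP 7.1 does not mention.

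Three other places bear on Day 1:
- Protocol 10 says that AEs "will be recorded from the time the subject has signed the ICF until the subject's final study visit", so pre-dose events are captured.
- SAP 3.1 describes what precedes randomization: "On Day 1, eligible subjects will return to the study center for collection of baseline safety and efficacy assessments".
- Protocol 10.2 says that the investigator "will provide information on dates of onset and resolution, intensity, seriousness, frequency" and further items. Clock time of onset is not among them.

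**The concern.** A pre-dose event cannot have been caused by study drug. SAP 4.3.1 treats Day 1 assessments made before treatment as baseline, yet SAP 7.1, read literally, treats an AE from those same hours as treatment-emergent. SAP 7 also drops separate summaries of laboratory tests, ECGs and vital signs and relies on notable abnormalities being reported as AEs. An abnormality found at the Day 1 pre-dose visit and reported as an AE could therefore be baseline under one section and treatment-emergent under another.

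The AE tables are the only safety summaries left in the SAP, and only the Sentinel Cohort, planned as 4 subjects per arm, is summarized. In arms of that size one subject is visible in any row. SAP 8 allows independent programming as a check. Two programmers could each follow SAP 7.1 in good faith and classify the same event differently.

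**Working it through.** The plan states no figure on this point, so there is none to reproduce. The check sets the texts side by side and then sizes the effect.

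**1. How a Day 1 event is classified**

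| Day 1 event | SAP 7.1, date-only reading | SAP 7.1, date-and-time reading | Protocol Table 9 |
|---|---|---|---|
| Timed, before dose, does not worsen | TEAE | Not TEAE | Not TEAE |
| Timed, before dose, worsens after dose | TEAE | Not TEAE, unless the worsening is entered as a new AE | TEAE |
| Timed, after dose | TEAE | TEAE | TEAE |
| Onset time unknown | TEAE | TEAE (assumed) | Depends on true timing |

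The first row is the conflict with the protocol. The second shows that adding a time comparison alone would open a gap, because SAP 7.1 has no worsening clause. In the fourth row both readings agree. Under the date-only reading that special rule adds nothing, since every Day 1 event already qualifies. It has work to do only if known Day 1 times are compared with the time of dosing.

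**2. Whether such events can occur.** SAP 4.3.2 makes Day 1 the date of first dose. Baseline assessments and randomization happen earlier that day (SAP 3.1), and AEs are recorded from consent (Protocol 10). So a pre-dose window exists and its events are recorded.

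**3. Size of one reclassification.** Planned arm size is 4, so one subject is 1/4 = 25 percentage points. SAP 7.1 counts unique subjects, so a row changes only if the subject has no qualifying post-dose event in that row.

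**4. Chance that any pre-dose Day 1 event occurs.** The documents give no AE rate. Assume r new AEs per subject-week, half of Day 1 before dosing, and 8 subjects:
- expected events = 8 × (r/7) × 0.5
- chance of at least one = 1 − exp(−expected)

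| r per week | Expected events | Chance of at least one |
|---|---|---|
| 0.05 | 0.029 | 2.8% |
| 0.1 | 0.057 | 5.6% |
| 0.3 | 0.171 | 15.8% |

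As a cross-check, a per-subject probability of 0.02 gives 1 − 0.98^8 = 14.9% in the cohort, in line with the top rate (0.3/14 = 0.021 per subject). If the probability were 0.05, the figure would be 33.7%.

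**5. Chance that the any-TEAE row moves.** The affected subject must also have no event after dosing. Over a full 16 weeks at the same rates, the expected number of such subjects, which approximates the chance when small, is 8 × (1 − exp(−r/14)) × exp(−16r):
- r = 0.05: 8 × (1 − exp(−0.05/14)) × exp(−0.8) = 1.3%
- r = 0.3: 8 × (1 − exp(−0.3/14)) × exp(−4.8) = 0.1%

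The chance that a preferred-term or SAE row moves lies between these values and those in step 4, because the same term is less likely to recur after dosing than any event at all.

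**The case against.** The strongest case against is that SAP 7.1 does not set a date-only rule. It asks for an onset time and has a special provision for a missing one on the day of first dose, which makes sense only if known times are compared with dosing time. On that view the phrase is a slip that a programmer would read correctly. The inference about intent is fair and stands. A reader might conclude from the wording that pre-dose Day 1 events will be counted; the documents do not support so flat a statement. The operative sentence still names no time of first dose, so the inconsistency remains.

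A reader might also infer that onset times will often be missing because Protocol 10.2 lists only dates. That list is narrative and not a form specification, SAP 7.1 itself refers to onset time, and the imputation rules in SAP 4.3.4.1 are redacted. How common untimed events will be cannot be told.

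Finally, a reader might infer that a placebo-arm pre-dose event would mask a drug excess. One such event would raise the placebo row, so the rule is not conservative in every case. But it applies identically to both arms, and pre-dose events are independent of blinded treatment, so the expected between-arm difference from this source is zero. SAP 7 plans no hypothesis test on safety data. SAEs, fatal AEs and TEAEs leading to dose reduction are also listed individually.

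**Conclusion.** The point holds as a defect of wording with a small consequence. As written, SAP 7.1 admits pre-dose Day 1 events, contrary to Protocol Table 9; its own unknown-time sentence points the other way; and it leaves out worsening in severity. The visible text of SAP 9 does not report a changed TEAE definition.

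One affected subject moves a row by 25 points in a planned arm of 4, if that subject has no post-dose event in the row. Under the assumed rates, the chance that any such event occurs is about 3% to 16%. That is not the chance that a table changes: for the any-TEAE row it is about 0.1% to 1.3%. These figures rest on assumed AE rates, an assumed half-day window and full 16-week follow-up, none of which the documents supply. No inferential conclusion is affected. The edit is worth making because it is nearly free and concerns the only safety tables that remain.

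**What to change.** Reword SAP 7.1 so that a TEAE is an AE that starts, or worsens in severity, on or after the date and time of the first dose, keeping the 14-day upper limit. This restores agreement with Protocol Table 9 and removes the choice between two programs.

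For an event dated Day 1 with no onset time, query the site before database lock on whether it began before or after first dose. Keep the existing assumption of treatment-emergent only where this cannot be resolved. State in the SAP whether onset time and first-dose time are collected.

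List as non-treatment-emergent only those Day 1 pre-dose events that did not worsen after dosing. Listing every pre-dose event that way would remove events that the protocol counts.

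The cost is one sentence in the SAP and a few site queries on about 8 subjects.

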4.5. Benefit-Risk Assessment

SCN8A-DEE is a severe and rare neurologic syndrome caused by de novo missense variants in the SCN8A gene, which encodes the pore-forming alpha subunit of Nav1.6. Currently no therapies are indicated to treat SCN8A-DEE, and seizures in SCN8A-DEE patients are typically very resistant to existing ASMs. SCN8A-DEE patients are at risk for developmental delay, cognitive impairment, and life-threatening status epilepticus and SUDEP, and the lack of an effective therapy for these patients establishes a clear unmet medical need.

NBI-921352 is a potent, selective, small molecule inhibitor of Nav1.6 channels.

[figure not shown]
channels and the selectivity of NBI-921352 for Nav1.6 against other human Nav isoforms.

The DMC will monitor safety and tolerability data throughout the study. The current study includes a Sentinel Cohort of 8 subjects (4 NBI-921352 and 4 placebo). Once the Sentinel Cohort has completed the [REDACTED] titration period, an external, independent DMC will review safety, tolerability, and PK data before subjects are randomized in the Main Cohort. Based on the DMC review of the Sentinel Cohort data, the doses, weight groups, and dose titration targets in the Main Cohort may be modified but [REDACTED]

ASMs as a class are associated with potential risks, including cardiovascular effects, CNS effects including increased risk of seizures, an increased risk of suicidal thoughts or behavior, and hypersensitivity reactions. The current study includes vital signs assessments and centrally read 12-lead ECGs throughout the study to monitor for cardiovascular abnormalities, and subjects with clinically significant abnormal ECG findings or vital signs at screening will be excluded from the study.

Safety and tolerability will be assessed at each dose level by the investigator before a subject's dose is increased to the next dose level. Subjects who are unable to tolerate Dose Levels 1 or 2 for their weight group will be discontinued from study treatment. Beginning at [REDACTED] of the titration period, doses may be decreased to a lower, tolerated dose level based on safety and tolerability. Study procedures are in place to ensure that subjects are monitored appropriately for seizure

exacerbations. Treatment regimens and prevention strategies are included to address serious events, such as status epilepticus and nocturnal seizures, which may result in SUDEP.

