6.7. Procedures for Overdose

For this study, any dose of NBI-921352 greater than the subject's assigned dose level within a 24-hour time period will be considered an overdose. The current version of the Investigator's Brochure should be referenced for overdose information. There is no recommended specific treatment for an overdose but to provide supportive care if clinically indicated.

In the event of a suspected overdose, the investigator and/or treating physician should:

1. Closely monitor the subject for any AE/SAE and laboratory abnormalities and follow the AE reporting process. The Study Medical Monitor should be contacted for adverse events related to an overdose.
2. Document the quantity of the excess dose(s), as well as the date(s) on which the additional dose(s) were taken, if this information is available.

Subjects who overdose will be counseled on correct dosing and administration of study treatment. Decisions regarding study discontinuation, dose interruptions, or dose modifications will be made by the investigator in consultation with the Medical Monitor based on the clinical evaluation of the subject.

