After [REDACTED] of the titration period, the investigator may decrease a subject's dose to the lower tolerated dose level based on safety and tolerability. In addition to the assessment of safety and tolerability at the titration period study visits, the study site will contact the parent/caregiver by telephone call approximately 1 week after the dose titration visits for Dose Levels 3 and 4 (ie, at the end of [REDACTED] to assess for any adverse events. Subjects who are unable to escalate to or tolerate Dose Level 2 should be discontinued from study treatment.

Once the Sentinel Cohort titration period has completed, the DMC will review safety, tolerability, and PK data as described in the DMC charter. Upon completion of the review and based on recommendations from the DMC, subjects may be randomized in the Main Cohort. Doses, weight groups, and dose titration targets in the Main Cohort may be modified based on the results of the Sentinel Cohort safety, tolerability and PK data; [REDACTED]

Subjects in both cohorts who complete the titration period will enter the [REDACTED] maintenance period. During the maintenance period, subjects will continue to receive their final tolerated dose from the titration period. Dose levels should not be changed during the maintenance period without prior Sponsor approval. Rescue medication is permitted at any time during the study and will not be a reason for discontinuation from study treatment. Following completion of the maintenance period, subjects will have the option to continue in the active extension study if they have successfully completed the 16 week treatment period ([REDACTED] titration and [REDACTED]

maintenance) in the current study and have not had a serious or severe adverse event (AE) that, in the investigator's opinion, was related to study treatment and would make it unsafe for the subject to continue study treatment dosing. For subjects electing to enroll in the active extension study, the last study visit will occur at the end of the maintenance period, and the first visit of the active extension study will occur at the same visit.

A complete schedule of assessments is provided in the study protocol.

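### SAP 7.1 has no category for adverse events that interrupt dosing or stop a planned dose increase, and the SAP reports no dose level reached, so titration stalled at Dose Level 2 or 3 cannot be seen by arm.

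*SAP*

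**What the plan says.** SAP 7 bases the Sentinel Cohort safety and tolerability evaluation on TEAEs and SAEs; other safety assessments are not summarized. In SAP 7.1 the overall table "summarizes the number and percentage of unique subjects with any TEAE, treatment-emergent SAE, TEAE leading to study drug dose reduction"; its action and outcome rows in full are "TEAE leading to study drug dose reduction, TEAE leading to study drug withdrawn, TEAE leading to study discontinuation, and TEAE resulting in death". It also shows intensity: "The summary table will also include the frequency distribution of the maximum TEAE intensity (mild, moderate, severe) reported for each subject". TEAEs are tabulated by system organ class and preferred term. The separate listings cover dose reductions, SAEs and fatal events.

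On titration, Protocol 4.5 states: "Safety and tolerability will be assessed at each dose level by the investigator before a subject's dose is increased to the next dose level". SAP 3 adds "Subjects who are unable to escalate to or tolerate Dose Level 2 should be discontinued from study treatment", lets the investigator step a subject down to a lower tolerated level after a redacted time point, and says that in maintenance "subjects will continue to receive their final tolerated dose from the titration period".

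Protocol 6.7 mentions "dose interruptions, or dose modifications" among the decisions that may follow an overdose. Protocol 10.2 has the investigator record "action(s) taken, changes in study treatment usage" for each adverse event, and Protocol 6.4 requires a dispensing record.

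**The concern.** The Sentinel Cohort was set up to examine safety, tolerability and exposure through a four-level titration. In such a design intolerance can show in three ways: treatment stops, the dose comes down, or the dose does not go up. SAP 7.1 has rows for the first two and none for the third, nor for a temporary interruption.

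Placebo follows the same schedule as NBI-921352, so the number of subjects in each arm whose escalation was blocked by an adverse event is a natural blinded comparison. The Main Cohort was not enrolled, so no later data from this study can supply it.

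**Working it through.** No sample size, power or alpha figure bears on this point, and SAP 7 plans no hypothesis test for safety. The check is therefore a comparison of the titration rules with the planned outputs, followed by a simple count.

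**Step 1. Where each titration outcome is counted, if a TEAE is the cause**

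| Outcome | Rule | Action-taken category in SAP 7.1 |
|---|---|---|
| Cannot reach or tolerate Dose Level 2 | Treatment discontinued (SAP 3; Protocol 8.1 for Levels 1 and 2) | Drug withdrawn |
| Stepped down to a lower level | Allowed after a redacted time point (SAP 3) | Dose reduction, also listed |
| Held at Level 2 or 3, no step-down | Follows from tolerability being judged before each increase (Protocol 4.5) and the final tolerated dose being carried forward (SAP 3) | None |
| Dosing interrupted, then resumed | Interruption named in Protocol 6.7, for overdose | None |

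**Step 2. Could another planned output show the last two?**

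- Disposition (SAP 5.1) reports completed or discontinued dosing. A held subject who finishes counts as completed.
- The listing of randomized subjects (SAP 5.1) gives weight group, not dose level reached.
- The SAP contains no exposure, highest-dose or final-dose summary, and no listing of all TEAEs with action taken.
- The interim analyses made for the DMC will be described in the study report, with no further summaries (SAP 6.1).

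None of these would show it.

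**Step 3. Count**

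Inputs: n = 4 per arm (SAP 3). Assume that k active-arm subjects are held at Level 2 or 3 by a TEAE, and that no subject in the arm has a TEAE leading to step-down, withdrawal, study discontinuation or death. The documents do not give k, so it is left to run from 0 to 4.

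- One subject: 1/4 = 25 percentage points.
- Each action or outcome row as planned: 0/4 for every k.
- Any-TEAE row as planned: at least k/4. The same events enter the SOC/PT tables and the intensity distribution.
- An added row for a planned escalation not made: k/4.

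For example, with k = 2 the four action or outcome rows read 0/4, the any-TEAE row reads at least 2/4, and the added row would read 2/4 = 50%. The any-TEAE row cannot separate these two subjects from two who had inconsequential events and reached Level 4. The value of k is an illustration, not an estimate.

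**The case against.** The strongest objection is that little is hidden. A reader who saw only the action rows might infer that an event blocking escalation falls in no row at all, and that an arm which failed titration would read as fully tolerated. The documents do not support either reading. The event is counted under any TEAE, by SOC and PT, and by intensity. Failure at Dose Level 1 or 2 because of an adverse event is counted as drug withdrawn, and step-downs are counted and listed as reductions. Nor does the planned table report non-escalation as zero; it does not report it.

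Other points also carry weight:

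- The study was terminated, and SAP 9 says that the report is synoptic and covers selected data.
- Protocol Table 9 promises no row for interruption or non-escalation, so no protocol commitment is broken. The SAP already goes beyond that table by adding dose reduction.
- The DMC was to review Sentinel Cohort tolerability unblinded.
- Interruption is named only in the overdose section, which is weak evidence that it was foreseen as a response to intolerance in titration.
- Parts of the titration rules are redacted, so holding a subject at Level 2 or 3 is inferred from the text that can be read.
- Protocol 10.2 gives no code list, so a withheld increase may not be a recorded value.

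These points limit the size of the problem and add some work to the fix. They do not supply an output that shows stalled titration. A synoptic report can be short and still say how far each of about 8 subjects was titrated.

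**Conclusion.** The gap is real but narrow. It covers subjects held at Dose Level 2 or 3 by an adverse event without step-down or withdrawal, and temporary interruptions; the case for the holds is the stronger of the two. Such events are reported as events, but their effect on titration is not.

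Each affected subject is 25 percentage points of an arm. How many were affected cannot be determined from the documents, so no figure for understatement is justified, and the run of k from 0 to 4 should not be read as one.

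The conclusion assumes that the redacted titration text does not require every blocked increase to be handled as a step-down or a withdrawal. If it does, only the interruption part remains. The change is worth making because tolerability through titration was a purpose of this cohort and is reported here from TEAEs and SAEs alone. It does not invalidate the planned tables.

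**What to change.** In SAP 7.1:

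1. Add two rows to the overall summary: *TEAE leading to study drug interruption* and *TEAE leading to a planned dose escalation not being made*.
2. Widen the dose-reduction listing to include both.
3. Add a by-subject listing, by arm, of highest and final dose level.

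Derive these from the adverse event eCRF information on changes in study treatment usage, cross-checked against the dispensing records. State the derivation before database lock and unblinding, in line with SAP 1.

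The cost is some SAP wording, two rows, a wider listing filter and one short listing. Non-escalation may not be a coded eCRF value, so its cause may need a blinded subject-level check for about 8 subjects. The drug may also look somewhat less well tolerated than in the current layout.
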